6.6.3. Secondary Efficacy Analysis

The secondary efficacy variables are HiSCR50, HiSCR90 and HiSCR100 at Week 16. The same primary efficacy analysis approach will be applied on the secondary efficacy variables.

Other secondary efficacy variables are percentage of subjects who experience HS flare through Week 16, percentage of subjects who achieved AN count of 0, 1, or 2 at Week 16 among participants with baseline Hurley Stage II, and percentage of subjects achieving at least 3 points reduction from baseline in NRS in Patient Global Assessment of Skin Pain at its worst at Week 16 among participants with baseline NRS ≥ 4 .

Analogous statistical hypotheses to the primary objective will be used for the secondary objectives.

6.6.3.1. Subjects Experiencing HS flare through Week 16

The secondary endpoints of percentage of subjects who experience HS flare through Week 16 will be analyzed analogously to the primary endpoint. HS flare will be determined programmatically at each assessment of AN count. To be counted as a HS flare, the AN count must increase from baseline by at least 25% and by at least 2 compared to baseline. A subject will be counted as having HS flare if they have a HS flare at any assessment after baseline, up to and including the assessment at Week 16 (including scheduled and unscheduled visits and early termination visits). The statistical null and alternative hypotheses to be used to assess these objectives are:

H₀: $\pi_{ABY} - \pi_{PBO} = 0$ H_A: $\pi_{ABY} - \pi_{PBO} \neq 0$

where π_{ABY} and π_{PBO} are the proportion experiencing HS flares through Week 16 among subjects randomly assigned to receive izokibep and placebo, respectively. One set of hypotheses will be tested for each dosing frequency of izokibep.

Subjects who received an oral antibiotic that could impact HS at any point before the Week 16 assessment will be included in the analysis with NRI (did experience HS flare). Subjects who have missing assessments will be included with multiple imputation, as described below.

The number and proportion of subjects for subjects who experience a HS flare in each treatment group will be reported, along with p-values, 95% CI without strata calculated using asymptotic Wald method will be reported as well. A bar plot showing the proportion of subjects experiencing HS flare for each treatment will be produced. Results will also be listed.

Multiple imputation will be used to impute data for subjects with missing data. The multiple imputation process will be the same the supplementary analysis defined in section 6.6.2 for HiSCR75, except that draining fistula counts do not play a role in flare and will therefore not be imputed when missing. Subjects with missing AN counts at any scheduled visit (week 4, week 8, week 12 and/or week 16) will have their abscess and inflammatory nodules counts imputed (separately) for each visit with missing data. The imputed counts will be summed and compared to criteria for flare. If the observed or imputed value at any visit meets the definition of flare, the subject will be counted as having a flare; otherwise, the subject will be counted as not having a flare. A total of 100 imputations will be imputed to form the complete data set with a pre-specified seed (3617627) to ensure reproducibility. These multiple imputed data sets are then analyzed by using the same method for the primary analysis for complete data as specified in Section 6.6.1. The final inference on treatment difference is conducted from the multiple datasets using Rubin's combining rules⁷. Other imputation, fully conditional specification method may be implemented if the multiple imputation model does not converge.

Note that NRI will not be used for the primary analysis of flare. The number of subjects with missing data may be larger than the number of subjects who experience a flare, so using NRI may result in an analysis dominated by missing data. A supportive analysis, described below, will be reported using NRI.

6.6.3.2. Hurley Stage II Subjects Achieving AN Count of 0, 1, or 2 at Week 16

The secondary endpoints of percentage of subjects with baseline actual Hurley Stage II who achieved AN count (including those lesions that had interventions before Week 16 and were no longer present at Week 16) of 0, 1, or 2 at Week 16 will be analyzed analogously to the primary endpoint. The statistical null and alternative hypotheses to be used to assess these objectives are:

H₀: $\pi_{ABY} - \pi_{PBO} = 0$ H_A: $\pi_{ABY} - \pi_{PBO} \neq 0$

where π_{ABY} and π_{PBO} are the proportion achieving AN count of 0, 1, or 2 at Week 16 among subjects randomly assigned to receive izokibep and placebo, respectively. One set of hypotheses will be tested for each dosing frequency of izokibep.

Subjects who have missing data at Week 16 or who received an oral antibiotic that could impact HS will be included in the analysis with NRI (did not achieve AN count of 0, 1, or 2). Only subjects with Hurley Stage II at baseline will be included in the hypothesis test for AN count, while other subjects will be summarized, and a p-value reported for descriptive use only. Methodology will be identical to that used for the primary endpoint with the exception of stratification factors. For the secondary endpoint, achieve AN count of 0, 1, or 2 at Week 16, which uses only subjects with Hurley Stage II at baseline, the stratification factor of baseline Hurley Stage will be omitted from the analysis. For the analysis using all subjects, the stratification factor of baseline Hurley Stage will be used, as in the primary endpoint analysis.

The number and proportion of subjects who achieved AN count of 0, 1, or 2 among participants with baseline Hurley Stage II in each treatment group will be reported, along with p-values, 95% CI without strata calculated using asymptotic Wald method will be reported as well. A bar plot showing the proportion of subjects who achieved AN count of 0, 1, or 2 among participants with baseline Hurley Stage II for each treatment will be produced. Secondary endpoint results will also be listed.

6.6.3.3. NRS of Skin Pain at Week 16

The secondary endpoint of percentage of subjects achieving at least 3 points reduction from baseline in NRS in Patient Global Assessment of Skin Pain at its worst at Week 16 among participants with baseline NRS \geq 4 will be analyzed analogously to the primary endpoint. Final, Version 3.0, 03APR2024 Page 42 of Hypotheses to assess percentage of subjects achieving at least 3 points reduction from baseline in NRS:

H₀: $\pi_{ABY} - \pi_{PBO} = 0$

 $H_A: \pi_{ABY} - \pi_{PBO} \neq 0$

where π_{ABY} and π_{PBO} are the proportion of subject achieve NRS Week 16.

The number and proportion of subjects achieving at least 3 points reduction from baseline in NRS in Patient Global Assessment of Skin Pain at its worst at Week 16 among participants with baseline NRS \geq 4 in each treatment group will be reported, along with a bar plot showing the proportion of subjects with baseline NRS \geq 4 who achieved NRS each treatment will be produced. Results will also be listed.

If a subject received certain prohibited analgesic therapy within 28 days of the visit (including the day of the visit), the subject will be imputed as a non-responder due to the ICE. A list of all subjects who took prohibited analgesic therapy which results in NRI will be created after the data is final and before unblinding, and will include justification for choosing the subjects based on specific analgesic, timing relative to Week 16, and other factors considered.

Since the NRS in Patient Global Assessment of Skin Pain is collected as a daily diary, the score used for analysis will be the average of the scores recorded 6 days prior to and including the Week 16 visit (7 days total for the average).

6.6.4. Supplementary Analyses for the Secondary Efficacy Analysis

For Part B, supplemental analyses of NRS pain will use MMRM among subjects with baseline NRS \geq 4, using observed change in NRS Patient Global Assessment of Skin Pain (average in the last 24 hours) at all scheduled post-baseline assessments up to Week 16. The model will include baseline NRS Patient Global Assessment of Skin Pain, visit week, treatment, and treatment by visit week interaction as covariates and will use an unstructured variance-covariance matrix. Other variance-covariance matrices, such as autoregressive, and compound-symmetric will be considered if the model does not converge. Sample SAS code is given as following:

proc mixed ; class week subjectid treatment(ref = "placebo") model change_y = baseline_y week treatment * week treatment repeated week / subject = subjected (treatment) TYPE = UN; lsmeans treatment * week /slice = week cl; slice treatment * week/ sliceby = week pdiff cl; run;

Another supplemental analysis of pain will be analogous but will use all subjects, including those with baseline NRS < 4.

Two supplemental analyses of flare will be reported. The first will impute any subject with missing AN count at any time after baseline as having a flare (missing = yes). The analysis will be analogous to that of the primary endpoint. The second will impute any subject with missing AN count at any time after baseline as not having a flare at that timepoint (but as having a flare if other observed data meet the definition of flare). This is equivalent to using only observed data for assessing flare. The analysis will again be analogous to that of the primary endpoint.

A supplementary analysis of HiSCR75 at week 16 will impute as non-responder any subject who received a new antibiotic or increased dose of antibiotic at any time after randomization and before week 16.

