4.1.2. Part B: Randomized, Double-blind, Dose-finding

Part B is a randomized, double-blind, placebo-controlled, parallel-group, dose-finding investigation to evaluate the efficacy, safety, and immunogenicity of izokibep in subjects with moderate to severe HS. Subjects will complete up to a 28-day screening period, followed by a 16-week double-blind treatment period. At completion of the Week 16 visit procedures, subjects randomized to placebo will be switched to active treatment in a blinded manner for the Week 16 dose through Week 30 (Q2W dose group) or Week 31 (QW dose group). Subjects randomized to izokibep will remain on the same dose through Week 30 (Q2W dose group) or Week 31 (QW dose group). After their respective treatment periods, all subjects will enter a follow-up period that includes 2 visits to be completed at Week 39 and Week 45. For subjects who early terminate, the follow-up visits should be completed 8 weeks (± 5 days) and 14 weeks (± 5 days) after the last dose of study drug.

Approximately 170 subjects will be randomized into 1 of 4 groups in a 1:1:2:2 ratio as follows:

- Group 1 (n = 28-29): placebo SC QW from Day 1 (Week 0) to Week 15, then izokibep SC 160 mg QW from Week 16 to Week 31.
- Group 2 (n = 28-29): placebo SC Q2W from Day 1 (Week 0) to Week 14, then izokibep SC 160 mg Q2W from Week 16 to Week 30.
- Group 3 (n = 56-57): izokibep SC 160 mg QW from Day 1 (Week 0) to Week 31.
- Group 4 (n = 56-57): izokibep SC 160 mg Q2W from Day 1 (Week 0) to Week 30.

Randomization will be stratified by any prior biologic/Janus Kinase (JAK) inhibitor use for HS (Yes/No) and Hurley Stage (II or III).

Subjects will complete study assessments according to the study visits outlined in the SoA.

Subjects in the QW dosing groups (Group 0 [Part A], Groups 1 and 3 [Part B]) will have study visits at screening, Day 1 (Week 0), and at Weeks 1, 2, 3, 4, 8, 12, 13, 14, 15, 16, 17, 20, 24, 28, and 32 as well as at the follow-up visits.

Subjects in the Q2W dosing regimens (Groups 2 and 4 in Part B) will have study visits at screening, Day 1 (Week 0), and at Weeks 2, 4, 8, 12, 14, 16, 18, 20, 24, 28, and 32 as well as at the follow-up visits.

Subjects assigned to placebo SC QW and placebo SC Q2W will be grouped together into a single placebo group for comparison to each dosing regimen of izokibep for Part B. The primary endpoint will be assessed at Week 16.

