Part B is a randomized, double-blind, placebo-controlled, parallel group, dose-finding investigation to evaluate the efficacy, safety, and immunogenicity of izokibep in subjects with moderate to severe HS. Subjects will complete up to a 28-day screening period, followed by a 16-week double-blind treatment period. At completion of the Week 16 visit procedures, subjects randomized to placebo will be switched to active treatment in a blinded manner for the Week 16 dose through Week 30 (Q2W dose group) or Week 31 (QW dose group). Subjects randomized to izokibep will remain on the same dose through Week 30 (Q2W dose

group) or Week 31 (QW dose group). After their respective treatment periods, all subjects will enter a follow-up period that includes 2 visits to be completed at Week 39 and Week 45. For subjects that early terminate the follow-up visits should be completed 8-weeks (\pm 5 days) and 14 weeks (\pm 5 days) after the last dose of study drug.

Approximately 170 subjects will be randomized into 1 of 4 groups in a 1:1:2:2 ratio as follows:

- Group 1 (n = 28-29): placebo SC QW from Day 1 (Week 0) to Week 15, then izokibep SC 160 mg QW from Week 16 to Week 31.
- Group 2 (n = 28-29): placebo SC Q2W from Day 1 (Week 0) to Week 14, then izokibep SC 160 mg Q2W from Week 16 to Week 30.
- Group 3 (n = 56-57): izokibep SC 160 mg QW from Day 1 (Week 0) to Week 31.
- Group 4 (n = 56-57): izokibep SC 160 mg Q2W from Day 1 (Week 0) to Week 30.

Randomization will be stratified by any prior biologic/Janus Kinase (JAK) inhibitor used for HS (Yes/No) and Hurley Stage (II or III).

Subjects will complete study assessments according to the study visits outlined in the SoA in the protocol. Day 1 corresponds to the first dose of study drug. All subsequent visits will be scheduled based on the Day 1 visit.

Subjects in the QW dosing groups (Group 0 [Part A], Groups 1 and 3 [Part B]) will have study visits at screening, Day 1 (Week 0), and at Weeks 1, 2, 3, 4, 8, 12, 13, 14, 15, 16, 17, 20, 24, 28, and 32 as well as at the follow-up visits.

Subjects in the Q2W dosing regimens (Groups 2 and 4 in Part B) will have study visits at screening, Day 1 (Week 0), and at Weeks 2, 4, 8, 12, 14, 16, 18, 20, 24, 28, and 32 as well as at the follow-up visits.

Subjects assigned to placebo SC QW and placebo SC Q2W will be grouped into a single placebo group for comparison to each dosing regimen of izokibep for Part B. The primary endpoint will be assessed at Week 16.

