- The third secondary endpoint, proportion of subjects who achieve at least 3 points reduction from baseline in NRS at Week 16 among participants with baseline NRS ≥4, comparing izokibep dosed QW to placebo dosed QW or Q2W.
- The third secondary endpoint, proportion of subjects who achieve at least 3 points reduction from baseline in NRS at Week 16 among participants with baseline NRS ≥4, comparing izokibep dosed Q2W to placebo dosed QW or Q2W.

If a null hypothesis is not rejected, p-values for subsequent hypotheses in the sequence will be reported as nominal, and will not be used to assess objectives or make determinations of efficacy.

For Part B, efficacy endpoints will be summarized by Period 1 and Period 2 separately. For Period 2, in general, no hypothesis test will be performed and p-value will not be reported. For binary endpoints, stratified tests will use the four strata from the randomization process. If a subject was incorrectly classified during the randomization process, the analysis will use the correct classification as recorded in EDC, not the classification used during randomization as recorded in IRT.

For each primary and secondary efficacy endpoint, the number and proportion of subjects achieving the endpoint in each treatment group will be reported by stratum and overall. Confidence intervals will be present with stratification (CMH weighting) and without stratification (Wald method). P-values will be reported for the stratified analysis. A bar graph showing the proportion of subjects achieving the endpoint for each treatment group along with the associated p-value will be produced. Results will also be listed.

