6.6.5. Exploratory Analysis

Exploratory endpoints will be analyzed analogously to primary and secondary endpoints with the same strategies for ICEs. Binary endpoints will be analyzed with a stratified test of risk difference and continuous endpoints will be analyzed with an MMRM model in general. Continuous data at timepoints before and including the primary timepoint will use all data from planned assessments up to and including the primary timepoint; continuous data after the primary timepoint will use all data from all planned assessments. Visit week, treatment group and interaction will be included in the MMRM model.

The number and proportion of subjects for binary endpoints in each treatment group will be reported, along with p-values, 95% CI without strata calculated using asymptotic Wald method will be reported as well. Results for continuous endpoints will presented as LS mean changes and associated SEs with associated 95% CI and p-values. For binary endpoints, a line plot showing the proportion of subjects experiencing such endpoints will be produced. For continuous endpoints, a line plot showing the LS mean and SE for each treatment group will be produced. Exploratory endpoint results will also be listed.

The following binary endpoints before or on Week 16 will be analyzed analogously to the primary endpoints of HiSCR75 at Week 16. The number and proportion of subjects for binary endpoints in each treatment group, p-values, 95% CI without strata calculated using asymptotic Wald method will be reported as well. The binary endpoints after week 16 will include number and proportion along with Clopper-Pearson 95% CI without strata according to the four randomized treatment groups. No p-value will be reported.

- HiSCR50, HiSCR75, HiSCR90 and HiSCR100 at Weeks 2, 4, 8, 12, 24 and 32;
- AN count of 0, 1, or 2 at Weeks 4, 8, 12, 24, and 32 among subjects with baseline Hurley Stage II;

- HS flares through Weeks 4 and 32;
- IHS4-55 response rates at Weeks 4, 8, 12, 16, 24 and 32;
- Draining fistula count of 0 at weeks 4, 8, 12, 16, 24 and 32
- Draining fistula count of 0 at weeks 4, 8, 12, 16, 24 and 32, among subjects with baseline draining fistula count of at least 1
- Draining fistula count of 0 at weeks 4, 8, 12, 16, 24 and 32, among subjects with baseline draining fistula count of at least 2

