6.6.7. Post-Week 16 (Part B, Period 2) Additional Analyses

The following analyses will be done for all four randomized treatment groups in the FAS:

- Proportion with at least 3 points reduction from baseline in NRS in Patient Global Assessment of Skin Pain at its worst, among subjects with baseline NRS ≥ 4, at weeks 24 and 32 will be summarized by number and proportion along with Clopper-Pearson 95% CI without strata according to the four randomized treatment groups.
 - NRI will be handled analogously to the corresponding secondary endpoint analysis, except subjects who took Tramadol as allowed per-protocol (at a dose of up to 100 mg po every 4 hours, not to exceed 400 mg per 24 hours) during the 28 days prior to the visit will not be counted as a non-responder.
- Descriptive MMRM analyses will be performed by randomized treatment group, for the continuous endpoints described below. The measured value at the visit will be used as the response variable, with visit week, treatment, and treatment * visit week interaction included as predictors. The model will include all visits from Day 1 through Week 32. Unstructured covariance matrix will be used. Other variance-covariance matrices, such as autoregressive, and compound-symmetric will be considered if the model does not converge. Estimated LSMean, corresponding SE values, and 95% confidence intervals will be summarized at the timepoints defined below.
 - Modified Sartorius Score at Weeks 24 and 32;
 - NRS PGA of Skin Pain (at its worst and average respectively) at Weeks 24 and 32. To maintain consistency between all visits, only the score collected on the visit day will be used for this analysis.
 - Draining fistula count at Weeks 24 and 32;
 - EQ-5D at Weeks 24 and 32;
 - DLQI at Weeks 24 and 32;
 - HADS, HADS-anxiety, and HADS-depression at Weeks 24 and 32;
 - IHS4 scores at Weeks 24, and 32

These summaries will address the question of expected results if a subject is assigned to either 32 weeks of izokibep or 16 weeks of placebo followed by 16 weeks of izokibep.

- A time-to-event analysis using Kaplan-Meier (KM) curves by randomized treatment group will be created for the events listed below.). If estimable, quartiles of the time to each event will be summarized by randomized treatment group. Product limit estimate at Week 32 (Day 224) will be provided. Participants will be censored at the time of last recorded assessment on study:
 - First achievement of HiSCR75
 - First achievement of HiSCR100

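### No repeated-measures model includes the two randomisation factors, and the supplementary pain model for the worst-pain endpoint analyses average pain

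*SAP*

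**What the plan says.** Protocol 4.1.2 states "Randomization will be stratified by any prior biologic/Janus Kinase (JAK) inhibitor use for HS (Yes/No) and Hurley Stage (II or III"), and SAP 2.1 repeats it. SAP 6.6 then carries the strata into one class of analysis: "For binary endpoints, stratified tests will use the four strata from the randomization process".

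The continuous endpoints use MMRMs, specified in three places.

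- **SAP 6.6.4** (supplementary pain analysis): "The model will include baseline NRS Patient Global Assessment of Skin Pain, visit week, treatment, and treatment by visit week interaction as covariates". The sample code agrees: "model change_y = baseline_y week treatment * week treatment". The response is described as "using observed change in NRS Patient Global Assessment of Skin Pain (average in the last 24 hours").
- **SAP 6.6.5** (exploratory): "Visit week, treatment group and interaction will be included in the MMRM model". Further down, the same section sends the continuous endpoints up to Week 16 to the 6.6.4 model. It asks for LS mean changes, standard errors, 95% confidence intervals and p-values.
- **SAP 6.6.7** (after Week 16): for the models covering Day 1 to Week 32, "The measured value at the visit will be used as the response variable, with visit week, treatment, and treatment" by visit interaction as predictors. The models for Week 16 responders and non-responders instead use change from baseline with the baseline value as a predictor.

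The secondary pain endpoint is a reduction of at least 3 points in worst skin pain at Week 16 among subjects with baseline NRS of at least 4 (SAP 2.5 and 6.6.3.3). Protocol 9.3.3 names an MMRM on change in pain score as a sensitivity analysis for it.

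**The concern.** A factor used to stratify randomisation normally goes into the analysis model. If it is prognostic and left out, the design has removed variance that the model still counts, so intervals are wider than they need be. The SAP itself treats both factors as informative. They are predictors in the multiple-imputation regressions of 6.6.2, and Hurley Stage III adds 9 points per region to the modified Sartorius score in Appendix 2, which is one of the MMRM outcomes.

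The pain item is a different kind of problem. A supporting analysis should address the same outcome as the endpoint it supports. As written, the 6.6.4 model addresses another diary question, and so does the second pain run, which is defined by analogy with it.

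**Working it through.** The plan gives no standard deviation, correlation or variance share for any continuous endpoint, so it has no figure of its own to reproduce on this point. Its one Part B power figure (SAP 2.3) concerns the binary primary endpoint: 15% against 40%, about 55 per arm, about 80% power. Exact enumeration with Fisher's test at two-sided 0.0499 gives 79.8%, and no MMRM enters it.

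**Step 1: model terms side by side.**

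| Model | Response | Baseline covariate | Strata |
|---|---|---|---|
| 6.6.4 pain | change, average item | yes, in text and code | none |
| 6.6.5 opening paragraph | continuous endpoints | not named | none |
| 6.6.5 list, up to Week 16 | change | yes, by reference to 6.6.4 | none |
| 6.6.7, all FAS subjects, Day 1 to Week 32 | visit value | no; Day 1 is a response | none |
| 6.6.7, Week 16 responders and non-responders | change | yes | none |
| 6.6.7, placebo subjects with AN count of at least 5 at Week 16 | visit value | no; Day 1 is a response | none |

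The last column is empty throughout.

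**Step 2: size of the strata omission.** Let R² be the share of residual variance that the strata explain, with arms balanced within strata. The reported standard error is then too wide by a factor of 1/√(1 − R²). The true size of a nominal two-sided 0.05 test is 2[1 − Φ(1.96/√(1 − R²))]. The R² values are assumptions.

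| R² | 1/√(1 − R²) | True size |
|---|---|---|
| 0.02 | 1.010 | 0.048 |
| 0.05 | 1.026 | 0.044 |
| 0.10 | 1.054 | 0.039 |

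**Step 3: pain item.** No arithmetic applies. The endpoint is worst pain, with baseline NRS of at least 4. The 6.6.4 model has the same restriction but uses average pain, and does not say which item defines the restriction. The 6.6.5 list does include worst pain, but as an exploratory endpoint. It states no baseline restriction and sets the score to 10 after certain prohibited analgesics. No listed MMRM combines the worst-pain item, the endpoint's population and observed change.

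**Step 4: Day 1 to Week 32 models on all FAS subjects (secondary matter).** With a free mean for each arm at each visit, Day 1 included, and complete data, the LS means equal the raw arm means. A generalised least squares check on simulated data (4 arms, 28 subjects each, 6 visits, estimated unstructured covariance) gave a largest difference below 1e-15. Having Day 1 among the responses therefore adjusts nothing when data are complete. For an assumed correlation r between baseline and Week 32:

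| r | SE ratio, unadjusted to adjusted difference, 1/√(1 − r²) | Carry-over of a 0.3 SD chance imbalance, 0.3r |
|---|---|---|
| 0.3 | 1.05 | 0.09 SD |
| 0.5 | 1.15 | 0.15 SD |
| 0.7 | 1.40 | 0.21 SD |

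For scale, the standard error of a baseline difference between 28 and 56 subjects is √(1/28 + 1/56) = 0.23 SD.

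**The case against.** The strongest reply is that nothing confirmatory depends on these models. Every test in the alpha-controlled sequence is a stratified risk-difference test on a binary endpoint (SAP 6.6, 6.6.1 and 6.6.3). Leaving out the strata makes intervals too wide, which cannot create a false claim. This stands, and it limits the point to a recommendation.

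Three stronger readings are tempting, and the documents do not support them.

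- *The exploratory models up to Week 16 ignore baseline.* The opening paragraph of 6.6.5 omits it, but the same section refers these endpoints to 6.6.4, which has it. What remains is a wording mismatch.
- *The 6.6.7 models as a group ignore baseline, so the Week 24 and 32 arm comparisons are compromised.* The responder and non-responder models adjust for it. The Day 1 to Week 32 models are labelled descriptive and report LS means, standard errors and intervals by arm. No between-arm contrast or p-value is specified, and SAP 6.6 says that in general there is no hypothesis testing in Period 2. The effect is confined to informal side-by-side reading of the arms.
- *Worst pain gets no repeated-measures analysis.* It gets one in 6.6.5. The differences in Step 3 are why that analysis does not replace the supplementary one.

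It is also fair to say that the documents supply no R² or correlation, and that at R² = 0.02 the gain is only 1%. A baseline-by-visit term would be a preference; its absence is not a defect.

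**Conclusion.** Two corrections are justified. First, no MMRM includes prior biologic/JAK use or Hurley stage. The consequence is a small, conservative loss of precision: standard errors about 1.0% to 5.4% too wide for R² from 2% to 10%. That range is assumed, as is balance of the arms within strata. It matters most in 6.6.4 and 6.6.5, which produce intervals or p-values. Second, the 6.6.4 pain model analyses a different item from the endpoint it is meant to support, and no other listed model fills that place.

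The lack of baseline adjustment in the Day 1 to Week 32 models on all FAS subjects is real, but those outputs are descriptive, so changing them is optional. Someone might infer from any of this that the primary or secondary conclusions, the type I error or the sample size are at risk. They are not.

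**What to change.** 1. In SAP 6.6.4, add prior biologic/JAK inhibitor use (yes/no) and Hurley stage (II/III) to the model text, and to the CLASS and MODEL statements of the sample code. The 6.6.5 models up to Week 16 then inherit them. If the factors are also carried into 6.6.7, drop the Hurley term in models restricted to Hurley II subjects, as 6.6.3.2 already does for the AN count endpoint.
2. In the opening paragraph of 6.6.5, name baseline among the model terms so that it agrees with 6.6.4.
3. In 6.6.4, run the pain MMRM on the worst-pain item among subjects with baseline NRS of at least 4, and state that the restriction uses the worst-pain item. Keep the average item as an additional run.
4. Optional: in the 6.6.7 Day 1 to Week 32 models on all FAS subjects, either model post-baseline values with baseline as a covariate or give the arms a common Day 1 mean. Leave the responder and non-responder models as they are. Do not impose a common Day 1 mean on the placebo subset selected by lesion criteria at Week 16, because that group is formed after randomisation.

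The cost is SAP wording, two model degrees of freedom for the two factors, and one extra pain run. Both factors are already collected, and SAP 6.6 already takes the correct classification from EDC. The edits should be made before treatment assignments are unblinded.
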